3.2 End-points

3.2.1 Primary endpoints

The primary endpoint the evaluation of postural stability and the weight distribution during a stabilometric task performed in "open eyes" and "closed eyes" conditions, and during a "voluntary swing" condition. The postural stability and weight distribution will be evaluated through two force platforms (P-6000 BTS SpA). The platforms will calculate the weight distribution between the two lower limbs and the antero-posterior and mid-lateral displacement of the Centre of Pressure (CoP) applied on the ground. An optoelectronic system with passive markers composed of six infrared cameras (Smart DX, BTS SpA) and 4-channel surface electromyography (FREEEEMG 1000, BTS SpA) will also be used. The markers will be placed on anatomic bony landmark according to the Davis model in order to reconstruct the pelvis, hip, knee and ankle kinematic on the sagittal plane during the stabilometric task [11]. The surface electromyography will be placed on the anterior tibialis and gastrocnemius medialis of both limbs, according to SENIAM recommendation in order to evaluate the muscles activations normalized respect to the maximum voluntary contraction (MVC), the timing of muscle activation respect to the movements of the tibiotarsic joint during the "voluntary swing" and the frequency of activation during the three trials [12].

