5.1 General Design

Unilateral THA and simultaneous bilateral THA patients will be recruited. They will be evaluated through three stabilometric tests, gait analysis, two strength tests, TUG and pain (NRS). The session trials will be done the day before surgery, seven and forty day after surgery. The stabilometric tasks, the two strength tests and the NRS will be performed also after three days. The stabilometric test will be characterized by "open eyes", "closed eyes" and "oscillations" conditions. The first two stabilometric tests ("open eyes" and "closed eyes") will last 45 seconds and will be repeated three times. Patients will be asked to keep the erected station with the parallel feet placed at an intermalleolar distance of 5 cm. Their arms should be relaxed along their sides. The patient has to maintain the balance looking at a point in front of him placed at 2 meters of distance in "open

eyes" condition. During the "oscillation" task, the subject, will be asked to perform three oscillations on the platforms, one after 10 seconds from each other. The gait analysis will consist of 4 trials in which the subject will be asked to walk on the gaitwalk. During the evaluation session all subjects will wear their underwear and the performance will be recorded through two cameras (eVixta, BTS SpA) in order to check the correct performance. Before the stabilometric tests and gait analysis, the two strength tests will be performed. In the first case patients will be asked to lie in supine position, to keep the hip with the knee completely extended up to 45 ° for 10 seconds. In the second case patients will be asked to lie on his side, to keep the hip abduction with extended knee for 10 seconds. Strength tests will be repeated for the two lower limbs both. The TUG before gait analysis, will consist of standing up from a chair, walking for 3 meters, to turning a cone and to sitting again, the operator will assess the time of the test. The TUG will be repeated for three times after a break of 1 minute and only the best performance will be considered. At the end of each single test the subject will be asked to quantify pain perceived through the NRS scale. This instrument consists of a visual 10 cm line, numbered from 0 to 10, where 0 corresponds to "no pain" and 10 to "maximum pain imaginable". All the tests listed will be performed by a single operator.

6 Statistical consideration

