6.1 Sample size

This protocol refers to a pilot study and therefore there aren't normative data. In literature we found studies evaluating the postural stability in THA patients, which enrolled 20 subjects [13]. For the following protocol, 30 subjects for each group will be considered in order to estimate the change of these parameters between-groups.

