6.2 Analysis

The statistical analysis will be performed at the end of the study through SPSS 20.0. Categorical variables will be described in terms of proportion, while the continuous variables will be described in terms of mean and standard deviation or median and interquartile ranges. Outcomes measures will be checked for normality through Kolmogorov-Smirnov test. T-Student test will be used to confirm the homogeneity of the demographic and continuous variables before surgery for stabilometric task (weight distribution between the two lower limbs, mid-lateral and anterior-posterior displacement of the CoP, pelvis, hip, knee and ankle kinematic, muscular activation normalized by MVC, timing of the muscle activation respect to the movements of the tibiotarsic joint and activation frequency) , during gait analysis (ground reaction force, spatio temporal parameters, pelvis, hip, knee, ankle kinematic and timing of muscles activation), during the segmental strength test (time of the support of the lower limbs in the position decided by the operator), related to the TUG (execution time of the trial) and to the NRS scale (value from 0 to 10). The inter-group and intra-group differences after will be evaluated by ANOVA test for repeated measurements and then an eventual post hoc analysis will be conducted. The statistical significance value will be set at $\alpha=0.05$.

7 Withdrawal of subjects

The patients that for any reason will decide to, they will be immediately excluded from it. The incompleting acquisitions will be excluded from the analysis.

8 Forms and procedures for collecting data and data managing

An Excel file (Attachment B) will be filled in with demographic variables and outcome measures. It will be secured by a password. Only two investigators will collect the data in order to reduce errors.

9 Ethical consideration

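### The primary endpoint is a domain tested at an unadjusted 0.05 with no deciding measure, condition or ANOVA effect; if any significant between-group change counts, the false-positive chance is about 8–14% (3 measures) or 12–37% (9)

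*Protocol*

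**What the plan says.** Section 3.2.1 gives postural stability and weight distribution as the primary endpoint, with eyes open, with eyes closed and during voluntary oscillation. On the measures it says: "The platforms will calculate the weight distribution between the two lower limbs and the antero-posterior and mid-lateral displacement of the Centre of Pressure". Kinematics and surface EMG during the same task are described in the same section.

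Section 5.1 sets the schedule: "The session trials will be done the day before surgery, seven and forty day after surgery". It adds: "The stabilometric tasks, the two strength tests and the NRS will be performed also after three days". Stabilometry therefore has four time points: the day before surgery and days 3, 7 and 40. The eyes-open and eyes-closed tests "will last 45 seconds and will be repeated three times", and the oscillation task has three oscillations. No rule is given for combining these repeats, although the TUG, a secondary test, has one (best of three).

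Section 6.2, repeated in the SAP, gives the analysis: "The inter-group and intra-group differences after will be evaluated by ANOVA test for repeated measurements". A possible post hoc analysis follows, with no method stated, and alpha is 0.05. Neither document names a deciding measure, condition or ANOVA effect, or gives a multiplicity rule.

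Section 6.1 says "This protocol refers to a pilot study" and takes 30 subjects per group "in order to estimate the change of these parameters between-groups".

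**The concern.** A primary endpoint should settle in advance which result answers the question. Here several results could, each judged at 0.05, and the plan does not say whether condition is analysed separately (nine variables) or as a within-subject factor (three outcomes). Nothing prevents the deciding result from being picked after the data are seen.

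The choice of ANOVA effect also matters. The aim is to compare recovery, which is change from before surgery. In a repeated-measures ANOVA that is the group-by-time effect. The group main effect averages over every visit entered, so if the pre-operative visit is included it mixes baseline status with recovery. The groups are defined by the operation the patients have, not by randomisation, so equal baselines cannot be assumed.

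**Working it through.** **Inputs from the documents.** Alpha 0.05 per test (section 6.2, SAP). Three platform measures and three conditions (section 3.2.1). Four stabilometric visits (section 5.1). 30 per group (section 6.1). The 0.05 is a chosen level and the 30 has no effect size, SD or power behind it, so neither is a figure that can be reproduced.

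**Assumptions.** The documents give no correlations between measures. I take a common correlation r of 0 (independent), 0.5, 0.7 and 0.9, and two-sided tests.

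**Step 1: number of tests.** 3 measures × 3 conditions = 9 if conditions are analysed separately; 3 if condition is a within-subject factor. One between-group test is counted per variable.

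**Step 2: chance of at least one p<0.05 when the groups recover identically.** For k independent tests it is 1 − 0.95^k:
- k = 3: 1 − 0.95³ = 0.143
- k = 9: 1 − 0.95⁹ = 0.370

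For correlated tests it is 1 − P(all |Z| < 1.96) for equally correlated normal statistics, by numerical integration.

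| Variables | Independent | r = 0.5 | r = 0.7 | r = 0.9 |
|---|---|---|---|---|
| 3 | 14.3% | 12.5% | 10.9% | 8.4% |
| 9 | 37.0% | 26.9% | 20.2% | 12.4% |

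**Step 3: check on the planned test.** Simulated group-by-time F tests under the null (30 per group, 4 visits, visit correlation 0.5 assumed, 20,000 runs, Monte Carlo SE at most 0.0035), in the same column order:
- 3 outcomes: 14.1%, 13.2%, 11.6%, 8.4%
- 9 variables: 36.9%, 27.7%, 20.9%, 13.5%

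These are within about one percentage point of the table.

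**Step 4: why the group main effect does not answer the recovery question.** Suppose recovery is identical but the groups differ by a constant gap g (in SD units) at all four visits. With visit correlation 0.5, the variance of a subject's four-visit mean is (1 + 3 × 0.5)/4 = 0.625. The standard error of the group difference is √(0.625 × 2/30) = 0.204. The chance that the group effect reaches p<0.05 on one variable, from the noncentral t with 58 df, is:
- g = 0.2: noncentrality 0.2/0.204 = 0.98, chance 16%
- g = 0.3: 1.47, chance 30%
- g = 0.5: 2.45, chance 67%

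The gaps are assumptions. A constant gap leaves the group-by-time test unaffected.

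**Step 5: precision.** The 95% CI half-width for a between-group difference is t × √(2/30), in SDs of the analysed measure (the change score, if change is used). For one primary test: 2.002 × 0.258 = 0.52 SD. For intervals matched to the first Holm step with two primaries (alpha 0.025): 2.301 × 0.258 = 0.59 SD.

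**The case against.** The best defence is that this is an observational pilot whose stated purpose is estimation, so error-rate control is beside the point. Much of that stands. Section 6.1 uses the pilot label and speaks of estimating change, section 2 offers the hypothesis as speculation, and no rule for declaring success is written anywhere. The figures above are therefore conditional: they apply only if any p<0.05 is presented as a primary finding. A reader might infer that the plan itself carries a 37% error rate; the documents do not support that. What does not stand is the idea that the pilot label settles the matter. It sits in the sample-size section, while section 6.2 and the SAP set a significance threshold with no limit on interpretation.

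It can also be said that the purpose in section 6.1, change between groups, already points to group-by-time. That is fair, but section 6.2 and the SAP do not say so.

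A reader might go further and count the group main effect as a second claimable test per variable, giving a much higher false-positive rate. That needs the groups to be equal before surgery as well as to recover identically. The documents do not support this: the groups are not randomised, and section 6.2 itself checks baseline homogeneity. No such figure is claimed here.

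Finally, counting 3 or 9 is a choice. It leaves out the kinematic and EMG variables in section 3.2.1, post hoc visit contrasts and group-by-condition interactions, so it neither describes every possible analysis nor sets an upper limit.

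**Conclusion.** The concern holds in conditional form. The plan tests a primary domain at an unadjusted 0.05 without saying which measure, condition or effect decides, and without saying that p-values are exploratory. If any significant between-group change is taken as a primary finding, the false-positive chance is about 8–14% for 3 measures and 12–37% for 9, against 5% for one named test. This rests on one test per platform variable and assumed correlations from 0.9 down to independence; even the most favourable of these cases exceeds 5%. Separately, a significant group main effect should not be read as different recovery, because a modest baseline gap can produce it alone. For a pilot this is worth correcting before analysis, but it does not call the design or the data collection into question.

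**What to change.** Amend sections 3.2.1 and 6.2 and the SAP in the same words.

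1. State that the between-group question is answered by the group-by-time effect (difference in change from the day before surgery), not by the group main effect. Report between-group differences in change with 95% CIs at each post-operative visit.
2. Then choose one of the following.
   - **Exploratory (simplest, and fits the pilot label):** state that all tests are exploratory and that no confirmatory significance claim will be made.
   - **Confirmatory:** name one platform measure in one condition, with how its repeated trials or oscillations are summarised, as the single primary test at two-sided 0.05. Alternatively, apply Holm across a short named list of platform measures and to their post hoc visit comparisons. Label everything else exploratory. The choice of measure and condition is the sponsor's.

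The cost is text only: no extra patients, visits or measurements, and the planned ANOVA is kept. The downside is that fewer results, or none, can be called significant. With 30 per group, precision stays at about 0.52 SD for a single primary test, but intervals matched to the first Holm step for two primaries widen to about 0.59 SD.

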14 REFERENCES10

1 Background and introduction

Total hip arthroplasty (THA) is an effective treatment for many hip joint diseases, able to improve patients' functional level and quality of life and to make the return to the activities of daily living possible [1] [2]. The improvement in surgical techniques had made the bilateral THA surgery possible, through one-stage procedure [3]. It seems not to be linked to increased in mortality rate or postoperative complications respect to the same two-stage procedure. [4] [5] [6].

The goal of the surgery is not only the pain relief, but also the functional recovery, which could take place through adaptive mechanisms of the non-afflicted limb. Simultaneous bilateral THA surgery doesn't allow these adaptive mechanisms and our clinical observation suggests that in this condition, the recovery of the operated limb could be faster. This is not a new hypothesis, in fact the use of the residual motor potential when adaptive strategies are not possible, has been largely demonstrated in the functional recovery of stroke patients [7]. In this case, the application of movement restrictions to the non-affected body segments and the intensive use of the affected side, promotes the motor and functional recovery [8]. Some authors suggest to apply similar approaches in other pathological conditions [9] [10].

2 Rationale of the study

Actually there are no studies investigating the motor and functional recovery of unilateral THA patients compared to simultaneous bilateral THA patients. Our clinical observation induce to speculate that simultaneous THA patients could achieve better functional and motor recovery of affected limbs caused by the impossibility to develop adaptive mechanisms with the contralateral side.

3 Object of the study

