3.1 General objectives

The aim of the study is to evaluate the lower limbs motor and functional recovery in subjects who undergone to unilateral o simultaneous bilateral THA.

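### Does the plan need a stated rule for which leg enters the repeated-measures ANOVA when an outcome is measured on each leg?

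*Protocol*

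**What the plan says.** Protocol section 6.2 lists the outcomes and then names one method: "The inter-group and intra-group differences after will be evaluated by ANOVA test for repeated measurements". The SAP repeats this and adds no rule about limbs.

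Several of the outcomes exist separately for each leg:

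- Strength hold time. Section 5.1: "Strength tests will be repeated for the two lower limbs both". Section 6.2 names the variable only as "time of the support of the lower limbs in the position decided by the operator".
- EMG. Section 3.2.1 has four channels for two muscles, and section 3.2.2 has eight channels for four muscles, so both legs are recorded.
- Hip, knee and ankle kinematics, and ground reaction force.

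On which limb is of interest, section 1 says that "in this condition, the recovery of the operated limb could be faster", and section 2 that "simultaneous THA patients could achieve better functional and motor recovery of affected limbs". Section 1 describes the other leg as the route of compensation: "the functional recovery, which could take place through adaptive mechanisms of the non-afflicted limb". The general objective in section 3.1 is worded more loosely: to "evaluate the lower limbs motor and functional recovery in subjects who undergone to unilateral o simultaneous bilateral THA". Section 6.1 sets the sample at 30 patients per group and aims to estimate change between groups.

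**The concern.** The two groups differ in how many operated legs a patient has. A unilateral patient contributes one operated and one non-operated leg; a bilateral patient contributes two operated legs. Averaging both legs in everyone therefore puts non-operated legs into one group only. Entering each leg as a separate case ignores the correlation between two legs of one person and makes the standard error too small.

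The direction of the averaging error is awkward. For hold time, where longer is better, an operated-leg deficit smaller at day 40 than before surgery would make bilateral patients appear to improve more even if operated legs recovered identically. That is the result the rationale predicts. A deficit larger than the preoperative one at day 3 or 7 would do the opposite. For EMG timing and kinematics the groups would differ with no clear better or worse direction.

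**Working it through.** The documents give no effect size, SD, power or between-leg correlation, so the plan has no figure to reproduce. Deficits and correlations below are assumptions.

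**1. Bias if both legs are averaged.** Let m(t) be the operated-leg mean at visit t, equal in both groups, and D(t) the amount by which the non-operated leg is better.

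- Unilateral average: [m(t) + m(t) + D(t)]/2 = m(t) + D(t)/2.
- Bilateral average: m(t).
- Spurious difference at a visit: D(t)/2. Spurious difference in change from baseline: [D(t) − D(0)]/2.

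Hold-time example, with the non-operated leg at 10 s and operated-leg means of 8, 4, 6 and 9 s before surgery and at days 3, 7 and 40:

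- Visit differences (unilateral minus bilateral): (10−8)/2 = 1 s, (10−4)/2 = 3 s, (10−6)/2 = 2 s, (10−9)/2 = 0.5 s.
- Differences in change: 3−1 = +2 s, 2−1 = +1 s, 0.5−1 = −0.5 s.

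If only operated legs are compared, the difference is m(t) − m(t) = 0 at every visit.

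**2. Effect on the planned test.** Simulated split-plot ANOVA, 30 per group, leg SD 1, same-leg correlation between visits 0.5, between-leg correlation rho = 0.3/0.5/0.7, no true difference in operated legs, both legs averaged:

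| Visits | Deficits (SD) | Group-by-visit significant |
|---|---|---|
| Four | 0.5/0.8/0.7/0.3 | about 13–17% |
| Three (no day 3, as for gait) | 0.5/0.7/0.3 | about 11–12% |
| Four | constant 0.5 | about 5% |

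The group main effect is significant more often (about 41/36/32% in the first row). Section 6.1 is about change, however, so group-by-visit is the relevant term.

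**3. Legs as separate cases.** With no limb difference, at one visit:

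- Operated legs only, 60 v 30: 2[1 − Φ(1.96 √(0.05 / ((1+rho)/60 + 1/30)))] = 6.2/7.0/7.8%.
- All legs, 60 v 60: 2[1 − Φ(1.96/√(1+rho))] = 8.6/11.0/13.3%.

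This is only a caution, since section 6.1 counts patients and not legs.

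**4. The reading the documents support.** Take operated limbs with one value per patient: the operated leg in unilateral patients and, in bilateral patients, either the mean of both legs or one leg fixed in advance. With the mean, group-by-visit type I error at 30 v 30 is 4.7–4.9%. A single leg is also valid, and its variance cost is (2/30)/((1+rho)/60 + 1/30) = 1.21/1.14/1.08, that is 21/14/8%. The choice left open therefore affects precision modestly and does not bias the comparison.

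Section 7 says "The incompleting acquisitions will be excluded from the analysis", so groups may end unequal. With 20 against 30 patients, in either direction, the type I error using the mean runs from roughly 3% to 7%.

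**The case for a change.** The best case for a written rule is that sections 1 and 2 are background, not an analysis instruction, and section 3.1 does not restrict itself to operated legs. Even if the operated limb is accepted, nothing says how a bilateral patient's two legs become one value. The authors did give such a rule for TUG, where the best of three trials counts. A few sentences would settle the matter and remove any chance of choosing the limb after seeing results.

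The omission stands. So does a related one: the index for weight distribution, which belongs to the primary endpoint, is not defined. It could be left/right, operated/other or absolute asymmetry. Operated/other has no meaning in a bilateral patient, and absolute asymmetry is the natural coding that means the same in both groups.

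What does not stand is the step from omission to error. The generic wording of section 3.1 does not contradict sections 1 and 2, and no passage proposes averaging in non-operated legs or counting legs as cases. The biased results in the working all come from analyses the plan does not prescribe. CoP displacement and TUG are one value per patient and are untouched.

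**Conclusion.** No change is needed. The plan leaves out a detail; it does not state a wrong rule. Its hypothesis points to operated limbs and its sample size to patients, and an analyst who follows both arrives at a comparison that holds about 5% with equal groups. The same planned ANOVA serves, with no new measurements. What remains open, the mean of two operated legs or one of them, is a choice between valid options that differ by 8–21% in variance.

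The figures of about 13–17% (four visits) and 11–12% (three visits) describe averaging both legs. They depend on assumed deficits that vary over time and on correlations of 0.3–0.7, and they fall to 5% if the deficit is constant. The judgement would differ if the documents prescribed averaging both legs or treating legs as independent cases. They do neither.

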OFFICIAL TITLE: Functional recovery after monolateral or bilateral total hip arthroplasty

PROTOCOL IDENTIFYING NUMBER: CLF17/02

DATE: 14/12/2017

Statistical analysis plan

The statistical analysis will be performed at the end of the study through SPSS 20.0. Categorical variables will be described in terms of proportion, while the continuous variables will be described in terms of mean and standard deviation or median and interquartile ranges. Outcomes measures will be checked for normality through Kolmogorov-Smirnov test. T-Student test will be used to confirm the homogeneity of the demographic and continuous variables before surgery for stabilometric task (weight distribution between the two lower limbs, mid-lateral and anterior-posterior displacement of the CoP, pelvis, hip, knee and ankle kinematic, muscular activation normalized by MVC, timing of the muscle activation respect to the movements of the tibiotarsic joint and activation frequency) , during gait analysis (ground reaction force, spatio temporal parameters, pelvis, hip, knee, ankle kinematic and timing of muscles activation), during the segmental strength test (time of the support of the lower limbs in the position decided by the operator), related to the TUG (execution time of the trial) and to the NRS scale (value from 0 to 10).

The inter-group and intra-group differences after will be evaluated by ANOVA test for repeated measurements and then an eventual post hoc analysis will be conducted. The statistical significance value will be set at $\text{Alpha}=0.05$.

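### The repeated-measures ANOVA, the only longitudinal method named, would in its classical form discard a patient's valid visits when one visit is unusable; a mixed model would keep them

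*Protocol*

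**What the plan says.** For differences over time, the SAP gives one sentence, repeated in Protocol section 6.2: "The inter-group and intra-group differences after will be evaluated by ANOVA test for repeated measurements", followed by post hoc tests if needed. The t-test is reserved for comparing the groups before surgery. Neither document names a mixed model or imputation, or says how the ANOVA treats a patient with a missing visit.

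Section 7 of the Protocol holds the only rule on incomplete data: "The incompleting acquisitions will be excluded from the analysis". It does not say whether the excluded unit is a recording, a task, a visit or a patient, and the SAP does not take the rule up.

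Section 5.1 sets the schedule. For the full set of tests, "The session trials will be done the day before surgery, seven and forty day after surgery". In addition, "The stabilometric tasks, the two strength tests and the NRS will be performed also after three days". Stabilometry, which carries the primary endpoint, therefore has four visits, while gait and TUG have three. Each quiet-standing test has three 45-second repeats, and "The gait analysis will consist of 4 trials". A rule for reducing repeats to one value is given only for TUG, where "only the best performance will be considered".

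Section 6.1 states that "This protocol refers to a pilot study" and takes 30 subjects per group "in order to estimate the change of these parameters between-groups".

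**The concern.** The classical repeated-measures ANOVA works on patients who have a value at every analysed visit. A patient whose stabilometry is unusable only on day 3 would drop out of that outcome's analysis altogether, although the values before surgery and on days 7 and 40 are sound. The more visits an outcome has, the more patients are exposed, so the primary measures are the most exposed.

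What is at stake is the precision of the estimate for which section 6.1 says the study is run. Section 6.1 makes no allowance for loss, so every deleted patient comes out of the 30. The undefined unit in section 7 could add to this: if one failed repeat were taken to spoil the visit, the ANOVA would then spoil the patient.

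**Working it through.** **Inputs from the documents.** 30 per group (section 6.1); four visits for stabilometry and three for gait and TUG (section 5.1); three repeats per quiet-standing test (section 5.1); alpha 0.05 (section 6.2, taken as two-sided).

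**Assumed, because the documents are silent.** Loss of 5% or 10% per visit, independent between visits; correlation 0.5 between visits; 80% power. At correlation 0.5 the SD of a change equals the SD of a single visit, since 2 × (1 − 0.5) = 1, so one SD scale serves for both.

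**The plan's own figure.** The 30 per group cannot be reproduced, because no difference, SD, power or dropout is given. For orientation, a two-sample t-test with 30 per group and no loss detects 0.74 SD.

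**Step 1: complete patients.** Expected number per group = 30 × (1 − m)^V, where m is the loss per visit and V the number of visits.

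| Visits needed | m = 5% | m = 10% |
|---|---|---|
| 4 (stabilometry with baseline) | 30 × 0.95⁴ = 24.4; 0.82 SD | 30 × 0.90⁴ = 19.7; 0.92 SD |
| 3 (gait and TUG with baseline) | 30 × 0.95³ = 25.7; 0.80 SD | 30 × 0.90³ = 21.9; 0.87 SD |
| 2 (gait and TUG, post-operative only) | 30 × 0.95² = 27.1; 0.78 SD | 30 × 0.90² = 24.3; 0.82 SD |

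The text does not say whether the ANOVA includes the pre-operative visit. If it does not, stabilometry moves to the three-visit row and gait and TUG to the two-visit row.

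**Step 2: valid visits thrown away.** With four visits and 60 patients, this is 60 × 4 × [(1 − m) − (1 − m)⁴]. At 5% it is 32.5 of 228 valid visits (14%); at 10% it is 58.5 of 216 (27%).

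**Step 3: a mixed model on the same data.** Weighting the information from every missing-visit pattern by its probability, the effective number per group for change from baseline to day 40 over four visits is 28.1 at 5% (0.76 SD) and 26.3 at 10% (0.79 SD). The listwise variance is 1.15 and 1.33 times as large (28.1/24.4 and 26.3/19.7). Correlations from 0.3 to 0.7 give 28.1 to 28.2 and 26.1 to 26.5. For three-visit outcomes the effective number is about 28 and 26, against 25.7 and 21.9.

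**Step 4: clustered loss.** If loss falls mostly on the same patients (latent correlation 0.8), complete patients over four visits are 26.8 at 5% (0.78 SD) and 24.2 at 10% (0.82 SD), so there is less for a mixed model to recover.

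**Step 5: the unit of exclusion.** Suppose 2% of recordings fail. If any failed repeat voids the visit and every visit is needed, 30 × 0.98¹² = 23.5 patients remain. If one valid repeat is enough, 30 × (1 − 0.02³)⁴ = 30.0 remain.

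**Step 6: what the mixed model does to bias.** Take a worst case in which exactly the lowest day-3 values are lost, 5% in one group and 20% in the other, with no true difference. The mean of a standard normal with its lowest 5% removed is 0.109, and with its lowest 20% removed 0.350.

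| Contrast | Complete patients only | Mixed model |
|---|---|---|
| Day-3 level | 0.350 − 0.109 = 0.24 SD | about 0.17 to 0.19 SD |
| Change, baseline to day 3 | 0.24 × (1 − 0.5) = 0.12 SD | about 0.17 to 0.19 SD |
| Change, baseline to day 40 | 0.00 | 0.00 |

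Deleting whole patients shifts baseline in the same direction as day 3, so part of the day-3 bias cancels in the change. The mixed model keeps the full, unbiased baseline, so its remaining day-3 bias passes whole into the change.

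**The case against.** The strongest reply is that nothing here is a demonstrated loss. The plan does not say which form of ANOVA or which SPSS procedure will be used, gives no loss rates, and describes a pilot with no power target. At 5% loss the change contrast moves only from 0.82 to 0.76 SD, and with clustered loss it would be 0.78 SD without any change to the method. All of this stands, and it is why the point is minor.

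In an instrumented study, an acquisition most naturally means one recording, and section 5.1 has performances filmed so that they can be checked. On that reading few visits would be lost. This is plausible, and no passage says that a failed repeat voids a visit. The 23.5 in Step 5 shows what the open wording allows, not what is planned.

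A reader might also infer that the plan biases the group comparison and that a mixed model would cure it. The documents do not support either part. Bias needs loss that is related to the outcome and differs between groups, and nothing in the text shows this. Even in the worst case, change from baseline to day 40 is unbiased under either method. In that worst case, deletion would shift the day-40 level by 0.12 SD, which using all available day-40 values removes; with equal loss the shift is zero. For change from baseline to day 3, the mixed model is the more biased of the two.

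**Conclusion.** The point holds as a minor, inexpensive improvement in precision. If the ANOVA is run in its classical form, independent loss of 5% or 10% per visit would leave 24.4 or 19.7 of 30 per group for the four-visit outcomes, where a mixed model would keep the equivalent of 28.1 or 26.3 for change from baseline to day 40. In detectable difference, that is 0.82 or 0.92 SD against 0.76 or 0.79 SD. These figures rest on assumed loss rates, independence between visits and a correlation of 0.5; clustering makes the gain smaller.

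Two stronger readings should be set aside. The plan does not state that patients with a missing visit are deleted; that is the likely result of the method it names. Nor do the documents show that the results would be biased, so the case for the change rests on precision.

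**What to change.** 1. In section 6.2 and the SAP, replace the repeated-measures ANOVA with a linear mixed model on all available visits, with group, visit and group-by-visit terms and an unstructured covariance. Say whether the pre-operative visit is included.
2. In section 7, apply the exclusion to the single failed recording and use the remaining valid repeats at that visit, so that neither the visit nor the patient is lost. State beforehand how the repeats are combined, for example as the mean of the valid ones with at least one required.
3. State the model's limit: it assumes that loss is at random given the observed data. Report missing day-3 tests by group and interpret the day-3 comparison with caution.

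Optional clarifications: how a trial that the patient stops early is classed, whether data collected before withdrawal are kept, and a code separating inability to perform from technical failure. The data file layout (Attachment B) is not among the documents reviewed and may already hold such a code.

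The cost is a few sentences and slightly more analysis work, with no extra patients, visits or tests. A visit value resting on one repeat is noisier than one resting on three. If day-3 loss depends on the unseen value and differs by group, the mixed model reduces bias in the day-3 level but increases it in change from baseline to day 3, as shown in Step 6.
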